Enrollment Criteria. Male and female adults with MetS (18-65 y) having no history of liver, cardiovascular disease, or cancer will be enrolled. They are expected to meet >3 established criteria for MetS,82 and we will enroll those fulfilling these specific inclusion criteria to improve participant homogeneity: fasting glucose (100-126 mg/dL), waist circumference (>89 cm or 102 cm for F/M), HDL-C (<50 or <40 mg/dL in F/M), triglyceride >150 mg/dL. Although elevated blood pressure is a symptom/criteria for MetS, only those individuals having blood pressure <140/90 mmHg will be enrolled to avoid those having with Stage 2 hypertension.⁸³ Age- and gender-matched healthy adults (19-25 kg/m²) will also be enrolled. They will be normoglycemic (glucose <100 mg/dL), normotensive (<120/80 mmHg) and normolipidemic (HDL-C >50 mg/dL or >40 mg/dL in F/M; triglyceride <150 mg/dL). Major exclusion criteria for all participants include: concurrent tea consumption (Camellia sinensis or herbal varieties); vegetarian; user of dietary supplements, prebiotics, or probiotics within past month; hemochromatosis; any gastrointestinal disorders or surgeries; chronic diarrhea; Parkinson's disease; smoker; alcohol consumption (>2 drinks/d); recent use of antibiotics or antiinflammatory agents. We will also not enroll any participants using any medications to manage diabetes, hypertension, or hyperlipidemia (e.g. statins, metformin, ACE inhibitors), any medications known to be contraindicated for use with green tea ingestion (e.g. antipsychotic medications [Clozapine, lithium, Diazepam], blood thinning medications [Warfarin], high blood pressure medications [nadolol], and monoamine oxidase inhibitors [selegiline]), women who are pregnant or lactating, or have initiated or changed birth control in the past 3 months.

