Power Calculation and Data Analysis. We performed a power analysis using serum endotoxin (day 28) as the primary outcome. Mean serum endotoxin of MetS and healthy adults was used to predict a conservative 30% improvement by GTE in MetS persons; this corresponds to a 10 EU/mL decrease in endotoxin in MetS. Simulations were used to estimate power based on 20 healthy and 20 MetS adults randomized to treatment vs control in a 50/50 ratio, respectively. Based on a linear model with treatment and health status, and within-subject measures, we will have >90% power (α =0.05) to detect the primary contrast of interest (GTE vs placebo in MetS adults) and additionally, >85% power (α =0.05) to detect an interaction between treatment and health status. Most data will be analyzed by linear mixed effects models (LMMs) with random effect for subjects (to account for repeated measures) and fixed effects for health status, gender, GTE treatment, time period, and their interactions. Multivariate regression analysis will define correlations between study variables with consideration of potential covariates. Statistical significance for all analyses will be set at P≤0.05.

C. Measurement/Instrumentation

Anthropometric Parameters and Blood Pressure. At screening, participants will rest for 15 minutes prior to determining blood pressure using an automated cuff. BMI will be calculated from height determined from a wall-mounted stadiometer and weight from a calibrated scale. Waist circumference will be assessed at the level of the umbilicus using a nonflexible measuring tape.

Blood Chemistries. At screening, fasting plasma glucose, triglyceride, and HDL-cholesterol will be measured by spectrophotometry utilizing validated clinical assays (Pointe Scientific). At day 0, 14, and 28 of the interventions, collected blood will be sent to The Ohio State University Medical Center for metabolic evaluations by assessing a serum chemistry panel [e.g. [e.g. liver function (aminotransferases), renal function (creatinine, BUN), CBC, glucose, insulin, insulin resistance⁷⁹].

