Overview of Study Procedures. Potential participants who call the study center in an anonymous manner for more information will be given a brief description about the study and asked a few questions to determine their eligibility (see Phone Script attachment). If they meet the eligible criteria, they will be invited to the study center for a screening meeting. During the meeting, the Informed Consent (see Informed Consent attachment) will be explained and provided for them to review. The participant will then be given the opportunity to review the Informed Consent form. If he/she chooses to participate in the study, they will be asked to provide written consent. After receiving informed consent, the participants' height, weight, waist circumference, and blood pressure will be measured. Additionally, a small fasting blood sample will be collected for blood chemistry analysis. If they are not fasted at least 10 hours), they will be asked to come back in the fasted state at a time of mutual convenience. These blood results in combination with anthropometric parameters will determine the participant's eligibility.

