Eligible participants who agree to proceed with the study will be invited to meet with a registered dietitian or trained research personnel at wk 0 (d 0), who will instruct them on how to complete a dietary food record and explain the details regarding following a low-polyphenol diet throughout the intervention. At this first visit, a fasting blood sample will be collected and the participants will be provided 2-wk supply of confections. They will be instructed to consume 6 confections per day. After 2 weeks, the participant will come in for a mid-intervention visit (d 14). A fasting blood sample will be collected and the participant will be provided another 2-wk supply of confections to complete the 4-wk intervention. Prior to the participants' last study visit, they will collect 3-d stool samples and return the samples or meet with study personnel to return their stool samples upon collection. At the end of the intervention (d 28), participants will visit the study and a fasting blood sample will be collected. Following this, participants will perform a gut permeability test. After completing the gut permeability test, participants will then follow about a 1-month wash-out period. Following the wash-out period, participants will repeat these procedures, except receiving the alternative study treatment (GTE, placebo) than what they previously received. We estimate that completion of all study procedures (2.4wk interventions and 1-month wash-out period) will take 10-12 weeks per participant. Each step of the study procedures will be discussed in detail below. See Study Design attachment for an overview of the study.

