Screening Meeting. Potential participants who have met the initial criteria of the study (based on the telephone interview) will be invited to the study center at a mutually convenient time. During this time, the participant and a member of the research team will meet in a private, quiet conference room or office. The individual will be provided the informed consent form, and its contents will be described to the potential participant. The participant will then have the opportunity to review it, and if they choose to participate in the study, they will be asked to provide written consent. Although the participant will be asked to sign the informed consent, the participant will be told that they will not be asked to participate if their body measurements, blood pressure, or plasma chemistries (see Enrollment Criteria) do not meet the study criteria. If the participant has provided consent, we will then measure the participant's height, weight, waist circumference, and blood pressure. Next, if the participant is fasted for at least 10 hours, we will ask if a trained individual can draw a small blood sample (15 mL; 1.5 tubes) so that we may measure blood chemistries (glucose, HDL, triglyceride). All samples will be coded to maintain participant anonymity. If the participant's anthropometrics, blood pressure, or plasma chemistries do not meet the study criteria, they will be told that do not meet the study criteria.

Potential participants who meet the criteria, will be contacted within a few days after their screening meeting to provide them with their blood and body measurement results and inform them of their eligibility to participate in the study. Consistent with our CLIA exemption, blood results will be

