
In the event that a participant is telephoned and is unavailable, a message will be left requesting a callback at a convenient time or that at a member of the study team will try calling again at a later time. No confidential or sensitive information will be shared with third parties or left on answering machines.

Intervention Timeline. Each participant will complete a 2-phase (GTE vs placebo) randomized, crossover study. Each study intervention will consist of 3 study visits (Day 0, 14, 28) over a 4-wk period. After completing the first intervention, participants will undergo a wash-out period (1 month), and afterwards, begin the alternative intervention.

On Day 0, participants will come to the study center in a fasted state and provide a blood sample (45 mL) to measure endotoxin, TMAO, LBP, sCD14, a panel of clinical chemistries, and catechins. Following the blood collection, participants will be instructed on how to complete a 3-d diet record as well as be informed about maintaining a low-polyphenol diet throughout the duration of the intervention. Participants will then be provided a 2-wk supply of confections, for which they will be instructed to consume 6 confections each day (2 confections/meal; 1 g GTE/d).

On Day 14, participants will return to the study center in the fasted state and return any uneaten confections. Another blood sample (45 mL) will be collected for measurement of biomarkers as described above. Participants will then be asked to complete another 3-d diet record and be reminded to keep maintaining a low-polyphenol diet.

Prior to the final visit on Day 28, participants will collect a stool sample during the preceding 3 days. Participants will collect their stool samples in the comfort of their home and will be asked to return the samples on ice or meet with study personnel to return the samples to the study center within 24 h upon

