Participants will be asked to consume 6 confections each day (2 with each meal) for 4 weeks. Consumption of 6 GTE-rich confections is equivalent to delivering 1 g GTE/d. At the first visit, participants will provide a fasting blood sample and then receive a 2-wk supply of confections. Halfway through the intervention (d 14), participants will visit the study center in a fasted state (10-12 h). Participants will return any leftover confections. After a 5 min stabilization period, a single fasting blood sample will be collected following procedures stated above. After collecting blood, the participants will be provided the final 2-wk supply of confections. At the conclusion of the intervention phase (d 28), participants will perform a gut permeability test and provide another fasting blood sample. Compliance will be evaluated based on the number of confections returned throughout the study as well as objectively by measuring catechin/catechin-metabolites in the plasma. To ensure randomization, a random number generator will be used to randomly assign the sequence by which the participant will complete each of the interventions.

Gut Permeability Test. On the morning of testing at d 28 of the intervention, participants will arrive at the study center after abstaining from food and only consuming water for 10-12 hours. A gut permeability test will be conducted as described⁸⁵. Upon arrival, participants will be asked to empty their urinary bladder. Subsequently, they will then be asked to ingest a drink containing 40 g sucrose, 5 g lactulose, 1 g mannitol, 1 g sucralose, and 1 g erythritol dissolved in water (250 mL). Within 2-hours after ingesting the sugar test beverage, participants will be asked to consume an additional 500 mL of water. Participants will be instructed to abstain from foods that contain artificial sweeteners during the 24-hour period. Urine will be collected from 0-5 and 6-24 hours in sterile containers with 10% thymol (inhibit bacterial growth). For each urinary collection period, participants will be provided 2-L urine collection bottles and a cooler with ice packs to store collected urine until they return their samples the next day.

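### Aminotransferases are not among the screening tests and are first drawn at the visit that dispenses the first confections, so participants given GTE first start it with no trial liver result

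*Combined protocol and SAP*

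**What the plan says.** **Screening.** Section III.C (Blood Chemistries) lists the screening analytes: "At screening, fasting plasma glucose, triglyceride, and HDL-cholesterol will be measured by spectrophotometry". Section III.D (Screening Meeting) gives the same three analytes. Section III.D (Overview of Study Procedures) then says of the screening sample: "These blood results in combination with anthropometric parameters will determine" eligibility.

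**Liver criterion.** Section III.B (Enrollment Criteria) admits MetS adults "having no history of liver, cardiovascular disease, or cancer will be enrolled". No aminotransferase limit is given.

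**First liver test.** Section III.A and Section III.C (Blood Chemistries) place aminotransferases in the serum panel drawn on Days 0, 14 and 28 of each phase. Section III.A gives safety monitoring as one purpose of that panel.

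**Dispensing.** Three places in Section III.D put the Day-0 blood draw and the first supply in the same visit. The Overview says: "At this first visit, a fasting blood sample will be collected and the participants will be provided 2-wk supply of confections". The Intervention Timeline, after describing the Day-0 draw and the diet instructions, says: "Participants will then be provided a 2-wk supply of confections". The Intervention Phase text says: "At the first visit, participants will provide a fasting blood sample and then receive a 2-wk supply of confections".

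**The concern.** A history question finds only disease that someone has already diagnosed. The protocol gives its own reason to doubt that this is enough here. Its Significance section says MetS is often without symptoms and left unmanaged, describes NASH as the liver's expression of MetS, and calls it the commonest liver disorder in Western countries. A person with raised aminotransferases and no known liver disease satisfies the written liver and blood-test criteria.

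The panel that could identify that person is drawn when the product is handed over, so it cannot inform the decision to enrol. If the sequence is GTE first, the participant is taking the active product before any liver value is known to the trial. At stake is a modest participant-safety gain and a liver criterion that does what it appears intended to do. The treatment comparison is not at stake.

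**Working it through.** **1. Is there any earlier draw that could supply a liver result?** Section III.D (Sampling Handling) gives 15 mL at screening, 45 mL on each of Days 0 and 14, 60 mL on Day 28, and a total of 315 mL.

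- Per phase: 45 + 45 + 60 = 150 mL.
- Whole study: 15 + 2 × 150 = 315 mL, which reproduces the stated total.
- Left for any other draw: 315 − 315 = 0 mL.

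The only blood taken before Day 0 is therefore the 15 mL screening sample, and its analytes are listed twice without aminotransferases.

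**2. Who is affected?** Section III.B (Power Calculation and Data Analysis) gives 20 MetS and 20 healthy adults and a 50/50 ratio. I read that ratio as the split between sequences. The split within the MetS group is then expected rather than guaranteed.

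- MetS, GTE first: 20 × 0.5 = 10.
- MetS, placebo first: 10. They have three phase-1 panels (Days 0, 14 and 28) before their first GTE.

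About 10 healthy participants are also GTE first, but the protocol's argument about silent liver disease concerns MetS, so no risk is argued for them.

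**3. What do they start taking?** Section III.A gives 1 g GTE a day, 82% catechins by weight, of which 63% is EGCG. The four listed catechin shares add up to 100% (63 + 18 + 10 + 9), so they are shares of the catechins.

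- EGCG per day: 1000 mg × 0.82 × 0.63 = 516.6 mg, about 517 mg.

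**4. How many have an undetected elevation?** Let q be the share of otherwise eligible MetS candidates above the chosen enzyme limit. The documents give no q. The chance of at least one such person among the 10 GTE-first MetS participants is 1 − (1 − q)^10. For assumed values of q:

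| q (assumed) | Chance of at least one |
|---|---|
| 0.5% | 4.9% |
| 1% | 9.6% |
| 2.5% | 22% |
| 5% | 40% |
| 10% | 65% |

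The answer is set almost entirely by the assumption. The table shows only that the size is unknown and is not an estimate.

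**The case against.** **This is a preference about how strict screening should be.** The product is food grade, phases last four weeks, and the dose is likened to about five servings of green tea a day. The protocol regards green tea as safe when used as recommended, expects no effect on ALT or AST, and cites human evidence of benefit in fatty liver disease. It also excludes heavier drinkers and users of drugs that conflict with green tea, and it repeats the panel at every visit. All of this stands, and it is why the point is minor. It does not make a history question able to find undiagnosed disease.

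**The Sampling Handling section names aminotransferases among the analyses of collected blood.** That list pools all visits. It also includes gene expression, which other parts of Section III.D tie to Day 28. It does not override the two specific screening lists.

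**Only major exclusions are listed, so a laboratory limit may exist elsewhere.** Possibly, but no test listed before Day 0 would supply the value.

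**Laboratory turnaround is not stated.** True. That GTE starts before a result is known is inferred from the visit order and the absence of any stated hold.

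Some stronger readings are tempting and should not be drawn:

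- *About one in five MetS participants is at risk.* The protocol's figure of about 20% is NASH prevalence in adults. It is not the share of eligible candidates above an enzyme limit.
- *Power will suffer.* The text contains no enzyme-based withdrawal rule, and nothing in it suggests that raised enzymes abolish an effect on endotoxin.
- *Renal function needs the same gate.* Creatinine is also first measured on Day 0, but the documents give no reason why it should decide who receives GTE.
- *Nobody reviews the panels or can stop treatment.* Such arrangements may sit in the consent form or attachments, which are not shown.

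**Conclusion.** The point holds in a limited form. As written, the first aminotransferase sample and the first supply of confections belong to the same visit, and no earlier blood is tested for liver enzymes. About 10 of 20 MetS participants are expected to begin about 517 mg EGCG a day with no trial liver result.

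This rests on reading the 50/50 ratio as the sequence split, and on the protocol's silence about holding intake until results return. How many of those 10 would have a relevant elevation is unknown. Expected harm is low. No bias is claimed, since each participant serves as their own control, and no loss of power is claimed. It is a cheap improvement that the sponsor could make, and nothing in the trial's validity depends on it.

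**What to change.** Add ALT and AST to the eligibility tests in Sections III.B, III.C and III.D (Screening Meeting):

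- Run them on the 15 mL screening sample already drawn, at the medical-center laboratory already used for Days 0, 14 and 28, and only for candidates who pass every other criterion.
- Before randomization, exclude anyone above a pre-set limit. Twice the laboratory's upper limit is one proposal, which would keep mild elevations in the MetS group. The sponsor may prefer another value.
- State that this limit is not subject to the best-fit rule in the Screening Meeting section. That rule lets someone just outside a criterion be enrolled, so without the exemption the new limit would not bind.
- Report the outcome in the existing eligibility call.

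The cost is at least 40 extra ALT/AST tests, one per enrolled participant, plus those for candidates the limit excludes. This compares with 40 × 3 × 2 = 240 full panels already planned. No new visit or draw is needed, only a short amendment before further screening. The drawbacks are slightly slower recruitment and a MetS group without marked enzyme elevation, which narrows the population a little.
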